***Descriptive statistics:***

We will calculate the mean and standard deviation of the following continuous measures:

- Area of available floor space indoors;
- Population density of indoor space (number of people dwelling in the home/total available area of indoor floor space);
- Height of stairwell railings (of those that had a railings); and

- Height of stove (of those who had stoves)

We will estimate the median and interquartile range of the following discrete measures:

- Number of rooms within the homes;
- Number of people who live in the home

We will generate tabular descriptions (frequencies and percents) of the following measures:

- Homes that had open stairwells (no railings);
- Homes that had minor (<1m^2) unfinished construction (of those who had unfinished construction);
- Those who had major (>1m^2) unfinished construction (of those who had unfinished construction);
- Building materials that the activity-facilitating items in the home are made of (e.g., clay, plastic, metal, wood, cloth, other).

We will use a mixed linear model with a random child-specific intercept. This is due to the repeated measures collected over the 7-day period for each participant. The physical activity data will be analyzed in activity counts per 15 second epochs, however to create multiple observations, we will nest the data by averaging the epochs over each of the 7 days to create 7 separate observations in each of the participant's datasets. This method was chosen since it will appropriately model the means and standard errors as well as properly handle missing data. We will use this model to estimate the unadjusted and multivariable-adjusted associations between each of the exposure variables (specified above) and PA level (counts/15s). Covariates that will be included in multivariable models will be pre-determined using a hypothesized directed acyclic graph (DAG).

***Objective #3: Estimate the associations between haemoglobin concentration (Hb) and preschooler physical activity level.***

To address our third objective, summary statistics (including mean, standard deviation, median, range, interquartile range) will be generated for hemoglobin (as a continuous variable) to help identify outliers and biologically implausible data.

Mixed linear modeling with a random intercept will then be used to determine the unadjusted and multivariable-adjusted association between infant hemoglobin and physical activity (mean counts/15s). Similar to objective #2, a priori covariates to be included in the multivariable model will be determined through the development of a DAG.

Using the same procedures identified in Objective #2, we will assess model assumptions and fit.

**Objective #4:** Describe sleep quantity and quality in the sample of preschool-aged children in urban Bangladesh

To address our fourth objective, we will create histograms of the distribution of the data to assess the spread and shape of the frequency distribution of the various available measures of sleep quantity and quality. The number of bins within the histogram will be determined using the equation  $1 + 3.3 \log_{10}(n)$ . A boxplot will then be created to assess the spread, as measured by the median; interquartile range (IQR); range of observations; presence of outliers; and provide additional information about the shape of the data. Finally, a Q-Q plot will be created to compare the frequency distribution of the data to a normal distribution. Using the shape and direction of the curvature, we will assess any deviation from normality.

We will then create summary statistics (including mean/standard deviation or median/range/interquartile range) for:

- Time spent in bed (hours)
- Time “to bed”, time “out of bed”
- Sleep quantity
  - Time at which “sleep onset”
  - Total Sleep Time (TST) (hours; min)
  - Total activity counts (cp60s)
- Sleep quality
  - Wake After Sleep Onset (WASO) (min)
  - Awakenings (number/sleep period); Avg awakenings (avg number/sleep period)
  - Movement Index (MI)
  - Fragmentation Index (FI)
  - Sleep Fragmentation Index (SFI)
  - Sleep efficiency (%)

We will also compare distributions across groups stratified by:

- Boys and girls
- BMI categories (underweight, normal, overweight and obese)
- Household food security status (food secure, moderately food insecure; severely food insecure)
- Anemic and non-anemic
- Other maternal and infant characteristics

We will then estimate the frequency of children who met Canadian physical activity 24 Hour Movement Guidelines recommendations on any day, and the average number of days on which children met the recommendations for sleep duration (10-13 hours/day). Bangladeshi recommended guidelines for preschool-aged children will be used if they are available at the

time of statistical analyses. These data will be compared to published results in similar international, preschooler populations.

This will be done using the same data files collected from the participant; however, we will only use data from non-waking hours. We will use the ActiLife software to analyze all nighttime activity data and derive variables pertaining to sleep quantity and quality.

We will also compare objectively measured sleep periods (based on accelerometry) with parent reported bedtimes and waking times. This will be done using Individual Manual Inspection (IMI) by comparing bedtimes and waking times reported in the Accelerometry & GPS Log to the computed activity and sleep graphs created in the ActiLife software.

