### *Primary Objectives*

The specific objectives of this study are to:

1. Describe physical activity levels in a sample of preschool-aged children in an inner-city community in Dhaka, Bangladesh,
2. Estimate the associations between characteristics of the physical environment of the home (total area of available floor space inside of the home, number and presence of

physical hazards, and the number of gross motor activity-oriented items present) and the physical activity levels of preschoolers in Dhaka, and

3. Estimate the associations between hemoglobin concentration (Hb) and preschooler physical activity level.
4. Describe sleep quantity and quality in the sample of preschool-aged children in urban Bangladesh

We hypothesize that low levels of preschooler physical activity are associated with a lack of play-oriented physical attributes (i.e., total area of indoor floor space, presence and count of unsafe physical hazards, and presence and count of stationary and portable gross motor activity-oriented items) within the homes in urban Bangladesh. We also speculate that low Hb may be associated with low physical activity levels in this population.

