We will use the cut-points established by Trost and colleagues:  $\leq 48$  cp15s for sedentary behaviour (SED), 49-418 cp15s for light physical activity (LPA), and  $>418$  cp15s for moderate-to-vigorous physical activity (MVPA) . These cut-points were chosen because they were derived from direct observation of a sample of toddler and preschool-aged children while wearing the ActiGraph GT1M accelerometer . Videos of the children playing were coded using a modified version of the Children's Activity Rating Scale before receiver operating characteristic curve analyses were conducted to determine the corresponding cut-points to the 3 categories of interest: SED, LPA, and MVPA . These results were found to exhibit excellent classification accuracy . They were then cross-validated against pre-existing cut-points that are established for toddlers and preschoolers, which were not found to be significantly different than the pre-established cut points established by Pate and colleagues  and those established by National Health and Nutrition Examination Survey .

We will then be able to calculate total time (minutes) as well as proportion of time (%) spent in each activity category (SED, LPA, MVPA). The overall mean cp15s for each child will be based on all 15-second epochs that occurred during eligible wear periods from the time that the caregiver indicated the child woke up until the time that the caregiver indicated the child went to sleep at. If this data is missing, we will use eligible wear periods between 8am to 8pm. This mean will exclude non-wear periods as defined above and when the accelerometer was not being worn by the child (based on daily logs collected from the caregivers via afternoon telephone call; Section 9.3.7.).

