- Mean cp15s on a day that is typically a work day (Sunday through Thursday)
- Mean cp15s on a Friday and/or Saturday (weekend)

For each of the above measures, we will also classify the activity in terms of average daily minutes and proportion of total time spent in SED state, LPA state, and MVPA state. In sensitivity analyses, we will compare the average daily minutes and proportion of total time spent in each activity category across different cut-off points that have been established by various research groups:

- Proportion of time spent in activity categories established by Pate and colleagues (SED:  $\leq 199$  cp15s; LPA: 200-419 cp15s; MVPA  $\geq 420$  cp15s)
- Proportion of time spent in activity categories established by Sirard and colleagues (SED:  $\leq 301$  cp15s; LPA: 302-614 cp15s; MVPA  $\geq 615$  cp15s) Proportion of time spent in activity categories established by Van Cauwenberge and colleagues (SED:  $\leq 372$  cp15s; LPA: 373-584 cp15s; MVPA  $\geq 585$  cp15s)

To address aim 4, we will analyze sleep quality and quantity directly on the nighttime accelerometry wear periods. Sleep data will be measured in 60-second epochs. This is obtained from the same accelerometry file that the activity data is derived from; however, data will be re-integrated into a 60-second epoch file (analyzes number of activity counts in every 60-second period).

Using the manufacturer's add-on to the ActiLife software (ActiLife 6 Full sleep Features Upgrade), we will be able to detect the number of sleep periods as well as the duration and quality of the sleep periods within the accelerometry file for each participant. The software will also detect and describe:

- Time in bed/out of bed (am/pm); duration in bed (hours; min)
- Sleep onset (when sleep commenced; am/pm)
- Total Sleep Time (TST; hours, min)
- Wake After Sleep Onset (WASO; describes how many minutes after sleep onset the participant woke up; min)
- Awakenings (number of awakenings during sleep onset)
- Average awakenings (average duration of awakenings during sleep onset; min)
- Total activity counts during sleep period (cp60s)
- Movement Index (MI)
- Fragmentation Index (FI)
- Sleep Fragmentation Index (SFI)
- Sleep Efficiency (%)

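### Objective 4 measures sleep at night only but scores it against a per-day target of 10-13 hours

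*Combined protocol and SAP*

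**What the plan says.** The fourth objective in section 7 is to "Describe sleep quantity and quality in the sample of preschool-aged children in urban Bangladesh". Section 10.1 (Outcome measure) sets the data source: "we will analyze sleep quality and quantity directly on the nighttime accelerometry wear periods". It then averages the sleep measures over each child's eligible nighttime wear periods. Section 10.4.1, Objective #4, repeats the restriction: "We will use the ActiLife software to analyze all nighttime activity data and derive variables pertaining to sleep quantity and quality".

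The same part of section 10.4.1 plans two summaries. One is the frequency of children who met the Canadian "24 Hour Movement Guidelines recommendations on any day". The other is "the average number of days on which children met the recommendations for sleep duration (10-13 hours/day"). Both are to be compared with published results in similar preschool populations.

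Two phrases are wider than night. Section 10.4.1 says "we will only use data from non-waking hours". Section 10.1 says of the software that "we will be able to detect the number of sleep periods as well as the duration and quality of the sleep periods" within each file.

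Section 9.3.6 lists the daily call items: morning wake time, belt removal in waking hours, time of going to sleep, and time away from home. There is no item on naps.

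**The concern.** The quantity measured and the target it is judged against have different time bases. The measure is sleep in nighttime wear and the target is hours per day. A night total can equal the daily total or fall below it, but cannot exceed it. A child who naps can therefore be put on the wrong side of either limit of the target.

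What is at stake is the headline sleep result: how often these children meet the recommendation, and how they compare with children elsewhere. If the published figures count sleep over 24 hours, a difference could reflect the definition rather than the children. A reader given the number without a night-only label could not tell. Objectives 1 to 3 do not use the sleep classification.

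**Working it through.** **Plan's own figures.** The plan states no figure for sleep or naps, so there is none to reproduce here. Its one computed figure, the 2.45 cp15s margin in section 9.6, does reproduce (1.96 × 9.7/√60 = 2.454), but it concerns mean activity counts.

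**Step 1: which nights are misclassified.** Let n be night sleep and k the nap, both in hours, with k no more than 3. As written, the plan scores a day as met if 10 ≤ n ≤ 13. If the target counts all sleep in the day, the right test is 10 ≤ n + k ≤ 13. The two disagree when:

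- 10 − k ≤ n < 10, which is wrongly failed;
- 13 − k < n ≤ 13, which is wrongly passed.

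| Nap (h) | Nights wrongly failed (h) | Nights wrongly passed (h) |
|---|---|---|
| 0 | none | none |
| 0.5 | 9.5 to <10 | >12.5 to 13 |
| 1 | 9 to <10 | >12 to 13 |
| 1.5 | 8.5 to <10 | >11.5 to 13 |
| 2 | 8 to <10 | >11 to 13 |

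**Step 2: how many days that could be.** This needs inputs that the documents do not give. Assumed: night sleep is normal with SD s = 0.75 h and mean m = 9, 10 or 11 h; a nap occurs every day; the target counts naps.

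- Wrongly failed = Φ((10 − m)/s) − Φ((10 − k − m)/s).
- Wrongly passed = Φ((13 − m)/s) − Φ((13 − k − m)/s).

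Example, m = 9 and k = 1.5: wrongly failed = Φ(1.333) − Φ(−0.667) = 0.909 − 0.252 = 0.656.

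Results for a 1.5 h nap:

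| Night mean (h) | Met, night only | Met, night + nap | Wrongly failed | Wrongly passed |
|---|---|---|---|---|
| 9 | 9.1% | 74.7% | 65.6% | 0.0% |
| 10 | 50.0% | 95.4% | 47.7% | 2.3% |
| 11 | 90.5% | 74.7% | 9.1% | 24.9% |

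Each row balances: night-only share + wrongly failed − wrongly passed = night-plus-nap share (for example 50.0 + 47.7 − 2.3 = 95.4).

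For a 0.5 h nap, the wrongly failed shares are 16.1%, 24.8% and 6.8%, and the wrongly passed shares 0.0%, 0.0% and 1.9%.

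**Step 3: fewer naps.** If half of days have a 1.5 h nap, unrelated to night length, the shares halve: about 33%, 24% and 5% wrongly failed, and 0%, 1% and 12% wrongly passed. With no naps both are zero.

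**The case against.** **The text may allow naps.** The reference to non-waking hours, and to the software counting sleep periods in the file, could be read to include daytime sleep. This has some force, and the wording is ambiguous to that extent. But section 10.1 opens the sleep analysis with nighttime wear and averages over nights, and section 10.4.1 follows its wider phrase with a nighttime one. No step forms a daily total. An ambiguity here would still need to be resolved in the text.

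**The target may not count naps, and the children may not nap.** The documents settle neither. This stands as a limit on the size. It does not remove the mismatch between a night measure and a per-day target.

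**A stronger reading of the activity data.** A reader might infer that naps also bias the primary outcome, mean cp15s, by more than the 2.45 margin. The waking window runs "from the time that the caregiver indicated the child woke up until the time that the caregiver indicated the child went to sleep at", with 8am to 8pm as the fallback, and has no nap rule. A restless or short nap can therefore stay in, mostly as sedentary time. However, the non-wear rule in section 10.1 removes still naps of 20 minutes or more. What remains depends on how much the child moves while napping and on the waking mean, and the documents give neither. Moreover, 2.45 is a sampling margin, not a tolerance for measurement bias. The documents do not support a claim of material bias, and no size is claimed.

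**Belt removal.** Section 9.3.5 lets caregivers take the belt off during sleep, but asks for it back on each morning. That points to overnight removal and should not be read as a nap provision.

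**Conclusion.** The point holds as a mismatch of definition in Objective 4. Followed as written, the plan scores night sleep against a daily target. If the target counts naps, it misclassifies any day on which the nap carries the total across 10 h or 13 h. The direction depends on night length: shorter nights produce false failures and longer nights false successes, so the net error cannot be signed in advance.

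The percentages illustrate what could happen and do not estimate what will. They rest on an assumed normal distribution, SD, mean, nap length and nap frequency, and they run from zero to about two thirds of days. The documents do not support saying that most children will be misclassified. Sleep is a descriptive objective, listed last in section 7 and absent from the primary objective and outcome in the Study Summary. The correction is worth making because it is nearly free, not because the study's main results depend on it.

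**What to change.** **Default.** In section 10.4.1, Objective #4, label the result as night sleep only and drop the met/not-met classification against 10-13 hours per day. State the night-only definition wherever the result is compared with published data. This is a wording change with no cost.

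**Alternative.** Keep night sleep as the main description. As a secondary result, compare night sleep plus software-detected daytime sleep with the target. This takes one further pass over files already processed for sleep. State its limits:

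- the documents give no accuracy figure for daytime detection, and there are no reported nap times to check against;
- quiet wakefulness may be scored as sleep;
- an unlogged belt removal may be scored as sleep, because it too is a run of zero counts;
- naps with the belt off are missed.

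The total can therefore be too high or too low, which is why the night-only label is the default.

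**Optional.** Add a sensitivity analysis of mean cp15s and sedentary time that excludes detected daytime sleep, with each child's valid days fixed beforehand so that none are lost. It carries the same limits and would show whether naps matter for the activity results. As wording only, state what makes a nighttime wear period eligible in section 10.1.

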### **9.3.6. Daily phone calls (caregiver)**

Every afternoon, study personnel will call the caregiver and go through a daily recall of (a) what time the participant woke up in the morning, (b) if, and when, the activity belt was removed during the participant's waking hours, (c) what time the participant went to sleep, and (d) if the participant left the home during the day (including location and duration away from home). This information will be documented in the Accelerometry & GPS Log each day. If a participant's caregiver cannot be reached on any particular day, study personnel will attempt to call 2 additional times that day. If contact has not been made, study personnel will contact the participant's caregiver the next morning and ask them to recall the previous day, then call again in the afternoon to recall the current day; a normal calling schedule will resume. If contact has not been made within 3 days, which has not been previously agreed upon between the participant's caregiver and study personnel (e.g., the participant is travelling, sick, etc.), the participant will be removed from the study and study personnel will visit the participant's home to collect the activity belt.

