For each child, we will calculate the mean number of minutes per day and the proportions of the child's total eligible wear time that are classified as SED, LPA and MVPA. We will also determine the proportion of days on which each child reached or exceeded 180 minutes of activity classified as LPA or MVPA, and the proportion of days on which each child reached or exceeded 60 minutes of activity classified as MVPA. These cut-offs are based on the Canadian preschooler physical activity guidelines established by Tremblay and colleagues , as there are no Bangladeshi standards available at present. If Bangladeshi guidelines are released before data analysis and reporting is completed, we will also apply those standards in our analyses.

For each child, we will establish the following parameters related to accelerometry:

- Total duration (minutes) of the potential data collection period on all days on which the accelerometer was instructed to be worn;
- Total eligible wear time (minutes), including data collected while the child was awake (from the time that their caregiver indicated that they woke up until the time that they went to sleep). If this data is not provided, total eligible wear time will be measured between 8am and 8pm. Non-wear periods will be excluded based on the following

criteria:  $\geq 20$  minutes of 0 cp15s allowing for up to 2 minutes of 0-100 cp15s in that period. A given day will be considered eligible for inclusion if there are at least 10 hours/day (600 min) between the indicated time period that the child was awake at, or between 8am to 8pm of wear time for those with missing data, after excluding non-wear periods;

- Total indoor eligible wear time (minutes; excluding non-wear periods as previously defined), based on maternal report;
- Total eligible wear time in or around the home (minutes; excluding non-wear periods as previously defined), based on combination of maternal report and GPS logging. "Around the home" will be defined as occurring in the same building or property of the home (e.g., rooftop, neighbouring apartment in the same building, common areas of the apartment building, private courtyard areas that are on the same property as the home in which the child resides).

For purposes of secondary and sensitivity analyses, we will also estimate for each child:

- Mean cp15s for indoor activity
- Mean cp15s for activity in or around the home

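### The sleep window is undefined; if it is the complement of caregiver-reported waking time, measured sleep can only be shortened and the comparison with caregiver report is not independent

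*Combined protocol and SAP*

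**What the plan says.** Objective #4 in Section 10.4.1 uses the same device files as the activity analysis, with one restriction: "however, we will only use data from non-waking hours". The term is not defined there or elsewhere.

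The plan's only operational waking window is in Section 10.1, where it sets eligible wear time for the activity outcome: "from the time that their caregiver indicated that they woke up until the time that they went to sleep". The fallback is: "If this data is not provided, total eligible wear time will be measured between 8am and 8pm". Both times come from the daily afternoon call (Section 9.3.6), which asks "what time the participant woke up in the morning" and "what time the participant went to sleep".

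Section 10.1 describes the sleep analysis in other terms. It says "we will analyze sleep quality and quantity directly on the nighttime accelerometry wear periods", again without limits, and that the software add-on will "detect the number of sleep periods as well as the duration and quality of the sleep periods within the accelerometry file". Times in and out of bed and sleep onset are listed as software outputs.

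Objective #4 then adds: "We will also compare objectively measured sleep periods (based on accelerometry) with parent reported bedtimes and waking times". This is done by manual inspection of the log against the software's activity and sleep graphs. Sleep duration is also judged against a target of 10-13 hours per day.

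**The concern.** The restriction in Objective #4 contrasts sleep with the activity analysis, so its most natural reading is the complement of the activity window, which means everything outside the caregiver's reported waking period. On that reading the log does two jobs. It decides which minutes can be scored as sleep, and it is then the comparator for the result.

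Two consequences follow. Sleep before a late-reported sleep time, or after an early-reported wake time, is removed before scoring, and no opposite error adds sleep back. Also, wherever the report cuts into true sleep, the scored boundary falls exactly on the report, so that disagreement disappears from the comparison. At stake are the total sleep time and guideline results of Objective #4, and the judgement on how well caregivers report sleep times.

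**Working it through.** The plan states no figure on this point, so there is none to reproduce. The check asks what a hard cut at the reported times would do.

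**Inputs from the documents.** The reported wake and sleep times are the only waking window (Section 10.1). The fallback waking window is 8am-8pm, so its complement is 24 - 12 = 12 h. The lower sleep limit is 10 h (Objective #4).

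**Assumed inputs.** The documents give no reporting error. Let e be the amount by which the report falls inside true sleep at one end: reported minus true onset, or true minus reported wake. Take e ~ N(b, s), with s = 15, 30 or 45 min. The bias b is 0 (unbiased), -30 (reported sleep window 30 min too wide at each end) or +30 (30 min too narrow). Detection is otherwise taken as perfect.

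**Formulas under a cut.**
- Scored onset = max(true, reported) and scored wake = min(true, reported), so the loss per end is max(e, 0), which is never negative.
- Mean loss per night = 2 × [s·φ(b/s) + b·Φ(b/s)]. For b = 0 this is 2 × 0.399s = 0.798s.
- Share of nights with exact agreement at one end = P(e > 0) = Φ(b/s).
- Mean absolute disagreement at one end = E|e| without the cut and E[max(-e, 0)] with it.

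**Numbers.** For b = 0: 0.798 × 15 = 12.0, 0.798 × 30 = 23.9 and 0.798 × 45 = 35.9 min. For b = -30, s = 30: 2 × (30 × 0.2420 - 30 × 0.1587) = 5.0 min. A simulation of 1,000,000 nights per scenario agrees. It also gives the last column, which further assumes true sleep with mean 10.5 h and SD 45 min; without a cut, 75% of nights reach 10 h.

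| Report | s (min) | Sleep lost per night (min) | Exact agreement at each end | Mean absolute disagreement per end, uncut to cut (min) | Nights reaching 10 h after cut |
|---|---|---|---|---|---|
| Unbiased | 15 | 12.0 | 50% | 12 to 6 | 65% |
| Unbiased | 30 | 23.9 | 50% | 24 to 12 | 56% |
| Unbiased | 45 | 35.9 | 50% | 36 to 18 | 48% |
| 30 min too wide | 15 | 0.3 | 2% | 30.3 to 30.1 | 75% |
| 30 min too wide | 30 | 5.0 | 16% | 35.0 to 32.5 | 71% |
| 30 min too wide | 45 | 13.6 | 25% | 43.6 to 36.8 | 64% |
| 30 min too narrow | 15 | 60.3 | 98% | 30.3 to 0.1 | 27% |
| 30 min too narrow | 30 | 65.0 | 84% | 35.0 to 2.5 | 28% |
| 30 min too narrow | 45 | 73.6 | 75% | 43.6 to 6.8 | 27% |

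The direction is the same in every row; the size depends almost entirely on the bias. Data cut at the report cannot show which row applies, because the sleep that would reveal a too-narrow report has been removed.

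**The case against.** A reader might infer that the plan defines the sleep window by caregiver report alone, so that sleep is cut short and agreement is built in. The documents do not support that. The non-waking period is never defined, the caregiver rule is written for the activity outcome, and that rule has a clock fallback. Section 10.1 has the software find sleep periods and in-bed times in the file, which would be largely redundant if the log had already set the limits. The word may simply mean night as opposed to day. The inspection also uses activity graphs, which may show movement, or its absence, outside the reported window. If caregivers report a window wider than true sleep, a cut costs little.

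Two further points are fair. The 12-hour fallback cap lies below the 13-hour upper end of the target, but by itself it fails no child on the 10-hour limit, and nights without reported times cannot enter the comparison. Also, scoring an uncut file has its own hazard: Section 9.3.5 lets caregivers take the belt off during sleep, and a motionless belt could be scored as sleep.

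All of this stands, and it makes the concern conditional. It does not remove it. Saying that sleep is detected in the file does not say the file is uncut, and the restriction in Objective #4 is an explicit rule about which data are used. Two analysts following the two sections could obtain different total sleep times from the same recordings.

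**Conclusion.** The concern holds in conditional form. Sections 10.1 and 10.4.1 describe the sleep window in different, undefined terms and must be reconciled. If the file is cut at the reported or fallback times, total sleep time and attainment of the 10-hour limit can only be biased down, and the comparison with the log is not independent. The loss ranges from near zero to about 74 min per night across the assumed scenarios, and is 12-36 min for unbiased error of SD 15-45 min. These are scenarios for a hard cut, not estimates for this study. The documents establish neither that such a cut will be made nor how large reporting error is. If no cut is intended, there is no such bias, and the sentence in Objective #4 misdescribes the analysis. Either way the text should change before the sleep analysis is run.

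**What to change.** In Objective #4, replace the restriction to non-waking hours with sleep detection on the full 60-second record, run without the log times, and state how the main night-time sleep period is identified. Make Section 10.1 say the same.

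Before scoring, exclude nights when the belt was off, by a stated non-wear rule. The daytime rule in Section 10.1 (20 minutes or more of zero counts, with a small allowance) should not be carried over unexamined, since a sleeping child can also be still for long periods. The daily call asks about belt removal in waking hours only, so the log cannot be relied on to identify these nights.

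Use the log only afterwards, as the comparator. Keep the graph inspection, and add the mean difference and 95% limits of agreement for sleep onset and for wake time, allowing for repeated nights per child. State that nights without reported times stay in the sleep description but not in the comparison.

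The cost is revised wording and some re-analysis of existing files; no new data are needed. Some nights will be lost to the non-wear exclusion, and their number should be reported.
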